Another problem with inpatient rehabilitation planning is the paucity of definitive clinical trials to inform the type of motor practice that should be administered. Constraint-Induced Movement (CI) therapy is arguably the most empirically-supported upper extremity intervention in subacute and chronic stroke, with strong evidence of increased effectiveness relative to standard care from the only positive definitively-powered upper extremity trial.^{15,16} Emerging evidence suggests that this is due to CI therapy being the only motor intervention to incorporate behavioral techniques designed to promote carry-over of training from practiced exercises to daily activities.^{23,24,26} These Transfer Package techniques include contracting, daily self-assessment of arm use, and problem-solving. Compared to other high-intensity dose-matched interventions that do not increase arm use for daily activities,²⁵ CI therapy combats learned nonuse, which translates into maintenance of therapeutic gains over time.^{50,51} Given that extent of carryover of motor training to daily activities is strongly associated with improved quality of life (but extent of motor improvement is not).²⁸ the carry-over techniques of CI therapy appear essential to optimal treatment success. The effects of these carry-over techniques in acute stroke have not been well established, however. With the exception of one study,⁵² all studies on acute CI therapy to date ¹⁷⁻ ²² omitted the behavioral strategies that promote carry-over of training, arguably the most essential components of CI therapy. Patient-centered research that seeks to adapt the CI therapy carry-over techniques to the inpatient rehabilitation setting is needed to foster increased acceptance and use of this approach.

Finally, there is the problem of inadequate and disparate continuity of care post-discharge,^{53,54} that particularly adversely impacts rural dwellers and other underserved communities.⁵⁵ Accordingly, function typically declines post-discharge (rather than continues to improve when intensive rehabilitation is available).^{12,13}

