This study will be conducted at the Minneapolis Veterans Affairs Medical Center (MVAMC). The MVAMC is home to the Stroke Specialty Program (SSP), a CARF accredited program. The SSP tailors rehabilitation for survivors of any stroke mechanism (hemorrhagic, occlusive, etc.) affecting any part of the brain. Services can be adapted for survivors with cognitive challenges. The SSP has averaged 41 admissions in the past three years, though 2017 has projected admissions over 50. Retrospective chart review demonstrates the primary diagnosis resulting from stroke to be hemiplegia in approximately half of the admissions. Most patients (85%) are older than 60 years, predominantly Caucasian (85%) or African-American (10%) and male (98%).

Recruitment: Prospective participants will be screened by a clinician. Patients meeting study criteria will begin the consenting process. We will attempt to recruit twelve subjects each year for a sample of 24. Assuming 20% attrition by 3-month follow-up, we anticipate a sample of 20.

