
Participants will begin playing the Recovery Rapids game when clinically appropriate per the clinician, at least 1 week prior to discharge. We anticipate at least three sessions with an OT will be devoted to teaching the game and personalizing game play to the individual. Though the exact dosing schedule will be refined based on stakeholder feedback gathered during preparatory work, game play will then occur independently outside of OT/PT sessions. Study clinicians will determine how often participants should engage in the game, with a general recommendation being 10-minute periods three times per day with the possibility for more gameplay on weekends. Recreation therapy staff will assist participants with game setup as needed. Participants will be asked to track how much time they spend on the game. Study clinicians will engage in adherence strategies that are typically used clinically with the participant to enhance use of the gaming system as needed.

Participants will have the option of wearing smartwatches (Figure 3) on both upper extremities targeting a wearing schedule of: all waking hours during the inpatient stay and 3-month follow-up. An app on the smart-watch uses accelerometer hardware to record the number of movements performed. The app also enables notifications (vibration coupled with $\hat{a} \in \mathbb{C}$ Please use me $\hat{a} \in \mathbb{C}$ text prompt) if the arm is not utilized for a period of 10 minutes. Notification will be set to $\hat{a} \in \mathbb{C}$ for the weaker arm and $\hat{a} \in \mathbb{C}$ for the stronger arm.

Figure 3: Smart-watch Biofeedback device.

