- 3) 18 hours independent game play is encouraged following discharge (30 min, 3 times weekly) over and above standard care (will be documented as covariate)
- 4) Use of smart watch with biofeedback

Retrospective Chart Review: We will conduct a chart review of Veterans who have participated in inpatient stroke rehabilitation at the Minneapolis VA over the past 5 years. Veterans whose charts will be reviewed will be identified by clinician members of the study team. We will review the medical records of each Veteran using CPRS and extract the relevant data. This will include demographic data (e.g. age, diagnosis, location, etc.), clinical data (e.g. outcome measures, interventions provided) and may include other clinical information as needed to adequately describe our sample. Data pulled from Veteran charts will be used as a retrospective control for the participants who receive the study intervention.

Approach to Aim 1: Determine the extent to which game-based CI therapy increases use of the more affected upper extremity from inpatient rehabilitation through subacute follow-up. For participants who use the smartwatch app, arm use will be tracked via a smart-watch app (see above) during the inpatient stay and post-discharge. Smart-watch biofeedback notifications for the standard care group will be set to $\hat{a} \in \hat{c} = \hat{a} \in \hat{c}$ for the weaker arm and $\hat{a} \in \hat{c} = \hat{a} \in \hat{c}$ for the stronger arm. Missing data (e.g., participant forgot to put the watch on one day) will be interpolated from data obtained during compliant days. The primary repeated-measures outcome will be total movement counts for each 1-week epoch from baseline through 3 months post-discharge (~12 weeks).

Approach to Aim 2. Pilot the clinical effectiveness and feasibility of distributed gaming CI therapy for improving motor function of the more affected upper extremity at 3 months post-

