During the at home portion of the study, training logs and smartwatch compliance logs will be employed. The study coordinator will call participants every two weeks post discharge, and as needed, until study participation has been completed. These phone interactions are intended to facilitate the proper use of the smartwatch device and to monitor self-reported compliance. The smartwatches will collect activity data on all subjects. There is a built-in data collection mode that allows for information on general activity level to be collected. Because the watches $\hat{a}\in^{TM}$ memory capacities are filled after one month $\hat{a}\in^{TM}$ s use, replacement watches will be sent approximately 3 weeks into the month of use to ensure that a replacement watch can be sent and received in a timely fashion. This will permit the next month $\hat{a}\in^{TM}$ s data to be recorded. The study coordinator will facilitate the exchange of the equipment in a timely manner so that there is no disruption in the data collection. During the telephone calls, subjects will be asked questions such as, $\hat{a}\in \mathbb{C}$ Have you taken either smartwatch off for any reason in the past two weeks? $\hat{a}\in \Phi$, $\hat{a}\in \mathbb{C}$ Have you received your replacement watch in the mail? $\hat{a}\in \Phi$.

Contact	Week	Approximate duration (minutes)	Remuneration	Administered by
Referral from Clinician	-1 or 0	5		PI, SC
Initial Study Contact	-1 or 0	15		SC
Consenting Process Initiated	0	60		SC

Table 4	Timetable	of Partici	nant A	etivity
1 abie 4.	Imetable	of I aftici	рані Ач	cuvity

Screening for Inclusion and Exclusion Criteria	0	15		OT or COTA, and SC		
Baseline Assessment	0	60	Х	A-OT		
Initial Gaming Set-Up	1	30		OT or COTA, PI, SC		
Standard of Care- Inpatient	1-3, 5x/week	30-60		OT or COTA		
Transfer Package- Inpatient	1-3, 3x/week	30		ОТ		
Gaming- Inpatient	1-3	10min 3x/day		OT or COTA		
Conclusion of Usual Care- Assessment	3	60	Х	A-OT		
Post-Discharge Home Visit to set up gaming system	3	60		PI		
Outpatient	Home Exercise Plan – varies dependent on individual patient progress					
Gaming- Outpatient	Gaming- Dutpatient3x/week30			Subject		
Follow-up Visit- Assessment	12	60	Х	A-OT		

OT- Occupational Therapist, A-OT- Assessor Occupational Therapist, COTA-Certified Occupational Therapy Assistant, SC- Study Coordinator, PI- Principal Investigator

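### Missing smartwatch data are filled from compliant days with no limit on the gap and no rule for the weeks after a participant stops wearing the watch

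*Combined protocol and SAP*

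**What the plan says.** The rule is in Research Design and Methods, Approach to Aim 1: "Missing data (e.g., participant forgot to put the watch on one day) will be interpolated from data obtained during compliant days". The same paragraph makes the total movement count in each one-week epoch, up to about 12 weeks after discharge, the primary repeated-measures outcome. It limits tracking to users of the app: "For participants who use the smartwatch app, arm use will be tracked via a smart-watch app".

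Other parts of the protocol bear on how often data will be missing:

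- The intervention description makes wear voluntary: "Participants will have the option of wearing smartwatches". The target is both arms, all waking hours, through the 3-month follow-up.
- Risks to Subjects, in the at-home part, states that "The smartwatches will collect activity data on all subjects". This sits awkwardly with optional wear and sets no rule for missing days. The same part describes two-weekly calls, compliance logs and replacement watches, because the memory fills after a month.
- Risks to Subjects also ends participation at discharge for those who could not set up the gaming system at home without in-person help.
- Recruitment expects losses: "Assuming 20% attrition by 3-month follow-up, we anticipate a sample of 20".

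The Statistical Analysis paragraph plans mixed effects linear models, or non-parametric equivalents, for the ARAT and possibly the Fugl-Meyer, WMFT and Neuro-QoL. It names no model for the weekly counts. It plans a comparison of those lost to follow-up with completers. That comparison does not cover someone who takes the watch off for good but attends the visit.

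**The concern.** The one-day lapse illustrates the rule but does not bound it. Nothing in the protocol defines a compliant day, sets how many worn days make a week usable, caps the gap that may be filled, or says what happens once wear ends. Voluntary all-day wear for about three months makes long gaps and permanent stopping foreseeable.

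For a participant who stops, every compliant day lies in the past. If the rule is applied to the remaining weeks, it carries an earlier level forward, and those weeks can show no change in arm use whichever way it went. The filled values are computed from data already in the series. They add no information, yet they would enter a repeated-measures analysis as if measured.

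Aim 1 asks about arm use from the inpatient stay through subacute follow-up, so the late weeks are the ones that matter. How many participants keep wearing the watch is also a feasibility result for this pilot, and unlimited filling would conceal it.

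**Working it through.** **The plan's own figure.** Planned sample 24 ("We will attempt to recruit twelve subjects each year for a sample of 24"), attrition 20%: 24 × (1 − 0.20) = 19.2, against a stated 20. This agrees within rounding and is not in dispute. It shows that the plan itself expects about 4 or 5 participants (24 − 20 = 4; 24 × 0.20 = 4.8) to be lost before the last week.

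**Share of weeks filled.** Inputs: 12 weekly epochs after discharge (Approach to Aim 1); the watch is last worn in week w. Share filled = (12 − w)/12.

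- w = 4: 8/12 = 67%
- w = 6: 6/12 = 50%
- w = 9: 3/12 = 25%

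If the three inpatient weeks in Table 4 are counted too, the denominator is 15 and the shares are 8/15 = 53%, 6/15 = 40% and 3/15 = 20%.

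**Share of the change that is masked.** The protocol gives no counts, wear rates or expected change, so this is an illustration. Assume arm use indexed at 100 for three inpatient weeks, then changing linearly by a fraction f at week 12, with f negative for a fall and positive for a rise. The fill method is not named, so two are shown.

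- Fill with the last worn week: the change seen at week 12 is f × w/12, so the share masked is 1 − w/12.
- Fill with the mean of all worn weeks: the change seen is f × w(w + 1)/[24(3 + w)], so the share masked is 1 − w(w + 1)/[24(3 + w)].

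| Last worn week | Masked, last value | Masked, mean of worn weeks |
|---|---|---|
| 0 (discharge) | 100% | 100% |
| 4 | 1 − 4/12 = 67% | 1 − 20/168 = 88% |
| 6 | 1 − 6/12 = 50% | 1 − 42/216 = 81% |
| 9 | 1 − 9/12 = 25% | 1 − 90/288 = 69% |

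The fraction f cancels, so these shares are the same for a fall and for a rise, of any size. What was recorded up to week w is kept.

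**Group level.** Assume a proportion p of wearers stop at discharge and are filled at their inpatient level. The apparent mean change is the true change × (1 − p). A true change of 30% appears as 24% (p = 20%), 18% (p = 40%) or 12% (p = 60%), again in either direction.

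**A single missed day.** Under a linear change, the average of the days before and after equals the missing day, so the bias is zero. The fault lies in the missing limit and not in interpolation as such.

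**The case against.** The best defence is that the rule was never meant for long gaps. Its example is one day, and interpolation in the strict sense cannot run past the last observation. That may well be what the authors intend. But the text does not say so, and on that reading the weeks after wear stops have no rule at all. A long gap with worn days on both sides would still be filled without limit. The same clarification is needed either way.

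A reader might infer something stronger: that the rule hides any fall in arm use after discharge, and so biases the result toward sustained use. The documents do not support that.

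- A fall recorded while the watch is worn stays in the data; only change after the last worn day is affected.
- The background does say that "function typically declines post-discharge", but it describes usual care and contrasts it with continued improvement where intensive rehabilitation is available. Relevance to the VA mission adds that home-based treatment lessens the decline, and participants may go on gaming at home. If arm use rises, filling from earlier days understates it.
- Illness, readmission or low motivation as reasons for leaving the watch off are plausible, but the documents do not establish them.

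Three further points limit the stakes. Participants who never use the app need no filling. The calls, logs and watch exchanges should reduce lapses, although none of them decides which data are analysed. The study is a pilot, and Sources of Materials calls arm use a potential moderator; Approach to Aim 1 nevertheless makes the weekly count a primary outcome.

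**Conclusion.** The concern holds in limited form. The only rule for missing watch data has no stated bound, and it governs Aim 1's primary repeated-measures outcome. Applied as written to a participant who stops, it fills 67%, 50% or 25% of the 12 post-discharge weeks for a stop after week 4, 6 or 9. It masks whatever change follows the last worn day and presents filled weeks as observed. Read strictly, it leaves the weeks after stopping without a rule.

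The shares of weeks filled follow from the stated 12 weeks alone. The shares of change masked rest on an assumed linear change and an assumed fill method. The group figures also rest on assumed stopping rates. The realised size and direction of bias cannot be derived from the documents: decline is possible but not assured under the intervention. Effects on power or type I error cannot be computed either, since the plan states no alpha, effect size or standard deviation and names no model for these counts.

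**What to change.** Replace the sentence in Approach to Aim 1 with a bounded rule, and add the analysis it needs:

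1. Define a worn day. Interpolate only isolated unworn days inside a week that meets a prespecified minimum of worn days (for example 4; the sponsor should set it).
2. Leave as missing every week below that minimum and every week after the last worn day.
3. Name a mixed model for the weekly counts in the Statistical Analysis paragraph and fit it to the observed weeks.
4. Report the number wearing the watch in each week beside the counts, with the date of and reason for stopping, collected on the existing two-weekly calls.
5. Add one sensitivity analysis in which post-stop weeks are set both below and above the participant's last observed level by an amount stated in advance. It is needed because a mixed model on observed weeks still assumes that stopping depends only on what was recorded.

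The cost is protocol and analysis wording; the calls and compliance logs already exist. The downside is fewer usable late weeks and wider intervals, which reflect the information actually collected.

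### Aim 1 is worded as a treatment effect on arm use, but no comparator with watch counts is recruited or allocated, and the wear rule behind the weekly counts is incomplete

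*Combined protocol and SAP*

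**What the plan says.** **Outcome.** Approach to Aim 1 sets out to determine how far the therapy increases use of the more affected arm. It then says: "The primary repeated-measures outcome will be total movement counts for each 1-week epoch from baseline through 3 months post-discharge (~12 weeks". The sentence before it gives the rule for gaps: "Missing data (e.g., participant forgot to put the watch on one day) will be interpolated from data obtained during compliant days".

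**Who is tracked.** The smart-watch paragraph by Figure 3 makes wear a choice: "Participants will have the option of wearing smartwatches". All waking hours are a target. Approach to Aim 1 limits tracking in the same way: "For participants who use the smartwatch app, arm use will be tracked via a smart-watch app". The at-home paragraph under Human Subjects Involvement and Characteristics says instead that the watches gather activity data on every subject. Compliance logs and two-weekly calls on self-reported compliance are described there, for the at-home period.

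**Who is compared.** Recruitment describes one group: "We will attempt to recruit twelve subjects each year for a sample of 24". Retrospective Chart Review names the control: "Data pulled from Veteran charts will be used as a retrospective control for the participants who receive the study intervention". The chart data listed are demographics and "clinical data (e.g. outcome measures, interventions provided) and may include other clinical information as needed to adequately describe our sample". Yet Approach to Aim 1 also says "Smart-watch biofeedback notifications for the standard care group will be set to" (the settings themselves are garbled in the text and are not relied on here). The paragraph on standard occupational therapy speaks of two groups, and Protection Against Risk names a standard care group beside the CI therapy group.

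**Analysis.** The Statistical Analysis paragraph names the ARAT, Fugl-Meyer, WMFT and Neuro-QoL. It does not mention movement counts. Sources of Materials calls arm use a potential moderator.

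**The concern.** To say that a therapy increases arm use is to say what would have happened without it. That needs watch counts from people who did not receive the therapy, or a stated reason why the untreated course is known. The plan's background gives reasons to expect movement in either direction: it cites heightened plasticity in the first weeks after stroke, and it says that function typically declines after discharge. A single-group trajectory over this period could rise or fall without any treatment effect.

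The weekly count also depends on how long the watch is worn and on how unworn time is filled. If wear changes between the ward and home, the count can change while arm use does not. Because wear is optional, those who contribute counts may also differ from the other participants. At stake is whether the pilot's Aim 1 result is reported as evidence of effect or as a description of wearers.

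**Working it through.** **1. The plan's own figure.** Recruitment assumes 20% attrition from 24 and expects 20. 24 x (1 - 0.20) = 19.2, which agrees to within one patient. No power calculation, allocation ratio or second-group size is given. The point below does not depend on this figure.

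**2. The comparator, passages side by side.**

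| Place | What it implies |
|---|---|
| Recruitment | One sample of 24, no allocation |
| Table 1 | Gaming CI therapy only |
| Retrospective Chart Review | Control from past charts; watch counts not listed |
| Approach to Aim 1, notification sentence | A standard care group with watches |
| Standard occupational therapy paragraph; Protection Against Risk | Two groups |
| At-home paragraph | Watch data on all subjects |
| Figure 3 paragraph; Approach to Aim 1, tracking sentence | Watch data only on those who choose to wear it |

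The first three rows describe a single treated group with a chart control. The next two need a second concurrent group, which no section recruits, sizes or allocates. The last two rows conflict with each other on coverage.

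**3. Wear: how far the count can move.** The documents give no worn hours or count rates, so these inputs are assumptions: a 14 h waking day, h hours worn, u = 14 - h unworn, and a = activity in unworn time relative to worn time.

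- True daily use is proportional to h + u x a.
- Error of a total with part-day loss unfilled: h / (h + u x a) - 1.
- Error of counts per worn hour: 14 / (h + u x a) - 1. A total filled at the worn-hour rate is that rate times 14, so it has the same error.

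| a | Unfilled total, h = 12 | Rate or filled total, h = 12 | Unfilled total, h = 10 | Rate or filled total, h = 10 |
|---|---|---|---|---|
| 0.2 | 12/12.4: -3% | 14/12.4: +13% | 10/10.8: -7% | 14/10.8: +30% |
| 0.5 | 12/13: -8% | 14/13: +8% | 10/12: -17% | 14/12: +17% |
| 0.8 | 12/13.6: -12% | 14/13.6: +3% | 10/13.2: -24% | 14/13.2: +6% |
| 1.0 | 12/14: -14% | 0 | 10/14: -29% | 0 |
| 1.25 | 12/14.5: -17% | 14/14.5: -3% | 10/15: -33% | 14/15: -7% |

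The two absolute errors are u x a / (h + u x a) and u x |1 - a| / (h + u x a). They are equal at a = 0.5 for any h. Above that the rate is closer to the truth; below it the unfilled total is closer.

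**4. Whole missed days.** With m unworn days in 7, the error of interpolation is 7 / ((7 - m) + m x a) - 1, which is also the error of a mean over valid days.

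| a | m = 1 | m = 3 |
|---|---|---|
| 0.2 | 7/6.2: +13% | 7/4.6: +52% |
| 0.5 | 7/6.5: +8% | 7/5.5: +27% |
| 0.8 | 7/6.8: +3% | 7/6.4: +9% |
| 1.0 | 0 | 0 |
| 1.25 | 7/7.25: -3% | 7/7.75: -10% |

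These are errors for one week. If the wear pattern and a stay constant, they cancel in relative change between weeks. They distort the trend when wear changes.

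**The case against.** Four stronger readings are tempting, and the documents do not support them.

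- **That wear is not corrected for at all.** The plan does state a correction, in the sentence just before the outcome. The missed day is given only as an example, so filling of part-days is not ruled out. The -14% and -29% figures apply only if part-day loss goes unfilled.
- **That no comparator with watches is mentioned anywhere.** The notification sentence and the at-home paragraph do imply one. What is missing is any recruitment, size or allocation for it, and any fit with the chart-review control.
- **That the outcome ignores which arm is meant.** The outcome sentence is silent, but the Aim in the same paragraph names the more affected arm. With watches on both arms, the definition only needs to say so.
- **That counts per worn hour should replace the primary outcome.** The tables show that this is not always better. At 10 h worn and 20% relative activity, which could arise if watches come off during rest, the rate is off by +30% against -7% for the unfilled total. A filled total has the same relative error as the rate. Worn hours may also be unavailable on the ward, since compliance logs are described only for the at-home period and nothing says that the watch exports wear time.

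It is also fair to say that this is a pilot and that a definitive comparison is left to later work. That lowers the stakes and keeps descriptive trajectories usable. It does not remove the problem, because the plan says the work will establish initial efficacy and words Aim 1 as an increase due to the therapy.

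**Conclusion.** The concern holds in this form. Under the only recruitment and control that the plan describes, a rise in weekly counts cannot be told apart from recovery over time, changes in wear or self-selection of wearers. It therefore cannot support a claim that the therapy increases arm use. This rests on the text alone and on no assumed figure. If a concurrent watch-wearing group does exist, the gap is instead that the plan does not describe it.

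The secondary point is conditional. Compliant days and part-day loss are undefined. If part-days are unfilled and the count per hour stays constant, a fall in wear from 14 to 12 or 10 h/day moves the total by -14% or -29%. Over relative activity of 20% to 125%, the range is -3% to -17% at 12 h and -7% to -33% at 10 h. All wear inputs are assumptions.

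This should be fixed before analysis. It limits what Aim 1 can conclude but does not invalidate the pilot.

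**What to change.** 1. **Reconcile the passages.** Bring the group wording in the standard occupational therapy paragraph, Approach to Aim 1 and Protection Against Risk into line with Recruitment and the chart-review control. Bring the optional-wear wording into line with the statement that watches collect data on all subjects. If no concurrent watch-wearing group exists, restate Aim 1 as within-participant change in weaker-arm counts among watch wearers, with no claim of effect against standard care. If one does exist, state how it is recruited and allocated, and its size.
2. **Complete the outcome definition.** State that the outcome is weaker-arm counts, set a minimum-wear rule for a compliant day, and apply the same fill-in rule to part-day loss. Report counts per worn hour as a supporting analysis where worn hours are available.
3. **Add a sensitivity analysis.** Set unworn-time activity below and above worn-time activity, over a range that reaches below 50%, for example 20% to 125%.

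**Cost.** If there is no concurrent group, this is wording and data processing, with no extra patients or visits. Some low-wear days drop out, and the Aim 1 claim becomes more modest. Worn hours may be unavailable for the inpatient phase, in which case the wear rule there may have to work on whole days.
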